### 6.3.2 Exclusion Criteria

- Other type of MS than highly active relapsing MS
- Contraindications listed in Cladribine 10 mg tablets SmPC.
- Moderate or severe hepatic impairment (Child-Pugh score  $>$ 6).
- Patient (men and women of childbearing potential) is unable or unwilling to practice birth control during Cladribine 10 mg tablets treatment and for at least 6 months after the last dose.
- Concurrent participation in any interventional study.

### 6.3.3 Withdrawal Criteria

- Withdrawal of patient consent
- Start of a new disease modifying drug
- Lost to follow-up

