	
performed using descriptive statistics: count (without missing), mean and its 95% confidence interval, standard deviation, median, minimum and maximum.
 
Interim analysis will be performed when all patients complete visit at month 25 or withdraw earlier.
 
A sample size of 85 subjects will have more than 80% power to achieve a supposed ARR 0.14 (95 % CI: 0.12–0.17) using a 2-sided significance level of 0.05. Assuming a 15% drop-out rate, a total of 100 patients will be targeted for this study.

Study Timelines:	
First patient first visit: April 2020
 
Last patient first visit: August 2021
 
End of data collection: October 2025
 
Enrolment period: 18 months
 
Participation of each patient will take approximately: 4 years (48 months). However, patients who postpone their therapy in year 2 due to low lymphocyte count up to 6 months (as per SmPC) are allowed to take part for up to 4.5 years in this case.

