## 4 STUDY OBJECTIVES

### 4.1 Primary

- To assess the effectiveness of Cladribine 10 mg tablets in the real life settings by the ARR^3 during the 4-year observational period.

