## 5 STUDY DESIGN

### 5.1 Description of the study design

This is a non-interventional, multicentre, prospective study for patients with highly active relapsing MS for whom Cladribine 10 mg tablets therapy was indicated independently before enrolment to the study. It is planned to enrol about 100 patients in 12 sites specialized for MS treatment in Slovakia (for sample size consideration please see Section 12.1).

Eligible subjects will undergo all visits and procedures before and during the treatment as per local standards and Cladribine 10 mg tablets administration will be in accordance with approved SmPC. There is no assessment mandated per study protocol. Management of disease including administration of rescue therapy and visit schedule are fully at the treating physician's discretion. Data for the study will be extracted from medical charts and entered into the electronic Case Report Forms (eCRF). Study assessments schedule (Table 8-1: Flow chart) is approximate, all described assessments and events will be collected and finally statistician will analyse them within relevant window for respective visit. According to standard practice in Slovakia, patients treated by DMD visit their physician at MS centre at least once per year (as required by payers) but usually every 3 months.

To collect high quality adherence data, patients will be asked to bring used/partially used Cladribine 10 mg tablets packages to the next visit after dosing and physicians will record number of actually used tablets, if Cladribine 10 mg tablets are not administered in the participating site as per standard practice.

Patients will be followed up to 4 years after the first dose of Cladribine 10 mg tablets. Patients with low lymphocyte count to start Cladribine 10 mg tablets therapy after the first year are allowed to postpone second cycle up to 6 months until lymphocyte count recovers (as per SmPC) and therefore their participation may take up to 4.5 years.

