## 7 EVALUATION CRITERIA

### 7.1 Primary endpoint

- ARR at 48 months

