### 7.2 Secondary endpoints

- Proportion of relapse-free patients at 24 and 48 months
- ARR at 24 months
- The time to sustained progression of disability from baseline up to 24 and 48 months
- Time to the first relapse from baseline up to 48 months
- Time to the second relapse from baseline up to 48 months

- Changes in mean number of T1 Gd+ lesions per MRI scan taken at 12, 24, 36 and 48 months compared to baseline
- Changes in mean number of active T2-weighted lesions per MRI scan taken at 12, 24, 36 and 48 months compared to baseline
- Changes in level of disability as measured by EDSS at 6, 12, 18, 24, 30, 36, 42 and 48 months compared to baseline
- No evidence of disease activity (NEDA-3) at 24 and 48 months
- The proportion of patients receiving rescue therapy according to local standards of care from baseline up to 48 months
- Patient adherence to Cladribine 10 mg tablets treatment after both dosing periods as assessed at 3 and 15 months (by counting used tablets from original packages as patients will be asked to bring them to the site).
- Frequency of adverse events interviewed or reported spontaneously by the patients or as noted on physical, MRI or laboratory examinations up to month 48
- Percentage of patients with at least 1 Common Terminology Criteria for Adverse Events (CTCAE) grade 3 or 4 Lymphocyte Toxicity up to month 48
- Median time to recovery from grade 3 or 4 Lymphocyte Toxicity
- Percentage of patients who developed herpes zoster infections or malignancies up to month 48

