### 12.2 Data Analysis

Analysis of collected data is based on descriptive statistics including absolute and relative frequencies of discrete variables. Continuous variables are described by count (without missing), mean and its 95% confidence interval (CI), standard deviation, median, minimum, and maximum. Discrete variables are described by count (absolute frequency), and percentages (relative frequency).

Missing data will not be replaced.

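### Ending study follow-up when a patient starts a new disease-modifying drug loses data that are probably outcome-related, and can make several, but not all, 48-month results look too favourable

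*Protocol*

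**What the plan says.** Section 6.3.3 has three withdrawal criteria: withdrawal of consent, loss to follow-up, and "Start of a new disease modifying drug". Table 8-1 provides a premature withdrawal visit that shares its column with the end-of-study visit. It covers MRI, EDSS, relapses and rescue therapy since the previous visit, adverse events, concomitant medication and the reason for withdrawal. Section 11 has adverse events collected until that visit. No later collection is described, apart from following up adverse events already detected.

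The study questions are not limited in the same way. Section 4.1 states the primary objective as ARR "during the 4-year observational period", and Section 7.1 gives the endpoint as "ARR at 48 months". Section 5.1 says: "Patients will be followed up to 4 years after the first dose of Cladribine 10 mg tablets". Section 7.2 includes "Proportion of relapse-free patients at 24 and 48 months" and "Time to the second relapse from baseline up to 48 months", as well as EDSS and MRI change, NEDA-3, sustained progression and safety endpoints up to month 48.

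On analysis, Section 12.2 says "Missing data will not be replaced", and the Protocol Summary has the primary analysis "performed using descriptive statistics: count (without missing), mean and its 95% confidence interval, standard deviation, median, minimum and maximum".

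**The concern.** Starting another drug and leaving the study are different events. The rule merges them, so follow-up stops at a moment the disease itself may have brought about. Disease activity on a previous drug is one of the two routes into this cohort (Section 6.3.1), so a later switch for activity on cladribine is a plausible pattern.

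If so, patients who are doing badly contribute less and less to the later time points, and the remaining patients look better than the treated cohort. The objective is real-life effectiveness over four years, for which patients who needed another drug matter most. A statistical analysis plan can choose an estimator or a censoring rule, but it cannot restore EDSS, MRI, relapse or safety data that were never extracted. This makes the point a matter for the Protocol.

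**Working it through.** **The plan's own figure.** Section 12.1 has 85 evaluable patients and 15% drop-out: 85 / (1 − 0.15) = 100, which reproduces. The 15% covers drop-out of every kind. The Protocol gives no separate switch rate.

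**Relapse-free at 48 months if only completers are counted.**

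- Inputs: ARR 0.14 (Section 12.1) and 4 years, so 0.14 × 4 = 0.56 expected relapses per patient.
- Assumptions: gamma frailty with variance 1; a fraction p of relapses leads to immediate withdrawal.
- True relapse-free: 1 / (1 + 0.56) = 0.64.
- Never withdrawn for a switch: 1 / (1 + 0.56p).
- Relapse-free among completers: (1 + 0.56p) / 1.56.

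| p | Withdrawn | Relapse-free, completers | True |
|---|---|---|---|
| 0.20 | 1 − 1/1.112 = 10% | 1.112/1.56 = 71% | 64% |
| 0.35 | 1 − 1/1.196 = 16% | 1.196/1.56 = 77% | 64% |
| 0.50 | 1 − 1/1.280 = 22% | 1.280/1.56 = 82% | 64% |

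Without frailty the true value is exp(−0.56) = 57%, and completers show exp(−0.56(1 − p)) = 64%, 69% and 76%. If relapses recorded before withdrawal are counted in all patients, this route gives no bias.

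**Other endpoints, by simulation.** Assumptions: true ARR 0.14 over 4 years; Poisson or gamma-mixed Poisson relapses (shape 1.0 or 0.5); withdrawal 3 months after a relapse with probability 0.3 or 0.6 per relapse. Between 13% and 27% of patients then switch, against the 15% allowed for all drop-out.

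| Quantity | Full follow-up | Withdrawal at switch |
|---|---|---|
| ARR, completers only | 0.14 | 0.04-0.10 |
| ARR, observed relapses over a fixed 4 years | 0.14 | 0.10-0.13 |
| ARR, pooled relapses / person-years | 0.14 | 0.11-0.14 |
| ARR, mean of patients' own rates | 0.14 | 0.21-0.28 |
| Relapse-free, completers only | 0.57-0.69 | 0.67-0.88 |
| Relapse-free, earlier relapses counted | 0.57-0.69 | 0.57-0.69 |
| Second relapse by month 48, crude proportion | 0.11-0.13 | 0.05-0.10 |
| First relapses lost | none | none |

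The mean of patients' own rates is too high because a patient who relapses early and leaves has a short denominator.

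**By reasoning.** Sustained progression needs an EDSS increase held for at least 3 months, and Table 8-1 schedules EDSS about every 6 months. A switch between the first rise and its confirmation leaves the progression unconfirmed. EDSS and MRI change at later visits, analysed as observed, omit patients who have left. Malignancy and herpes zoster endpoints run to month 48, but new events after the withdrawal visit are not collected.

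**The case against.** The strongest reply is that the failure prompting the switch is not lost. The withdrawal visit records relapse, EDSS and MRI, so a patient who relapses and then switches remains a recorded relapser and can be counted as a NEDA-3 failure. That stands.

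A reader might infer that the rule flatters every 48-month effectiveness endpoint. The documents do not support this. Time to first relapse is little affected when the relapse prompts the switch, the relapse-free proportion is unaffected if earlier relapses count, and ARR can be too low, about right or too high under an estimator the Protocol does not fix. A rescue-therapy effect depends on whether a new drug counts as rescue, which is not stated. Nor does the Protocol prescribe a completers-only analysis: not replacing missing data rules out imputation, but does not discard a relapse already recorded. Censoring methods and the coding of failures may properly be left to the analysis plan.

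It is also fair to say that switches for tolerability or preference need not flatter anything, that a switch may follow confirmed worsening because patients usually attend every 3 months, and that stopping at the switch would suit a question about outcomes while on cladribine alone. But no such question is stated. The objectives cover the whole period, and follow-up of up to four years does not by itself limit them to time before a switch.

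**Conclusion.** The concern holds in limited form. The rule discards follow-up that the stated four-year objectives call for, probably in relation to outcome. At risk of looking too favourable are observed-case EDSS and MRI change at later visits, NEDA-3 and relapse-free proportions if taken among completers, crude counts of second relapses, and progression awaiting confirmation. Safety follow-up to month 48 is shortened as well.

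The size is conditional. The 71-82% against 64% applies only to a completers-only analysis, with ARR 0.14, frailty variance 1 and 20-50% of relapses leading to withdrawal. The last two are assumptions without a source in the Protocol, as is the premise that switches mostly follow disease activity. For ARR, even the direction is open. The change should be made, because data not extracted cannot be recovered later.

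**What to change.** Remove the start of a new disease-modifying drug from the study withdrawal criteria in Section 6.3.3. Record it instead as an event with its date and the reason for the switch; Table 8-1 now lists only the reason for withdrawal. Continue extracting relapse, EDSS, MRI and adverse-event data from the chart to month 48 unless consent is withdrawn. Report 48-month endpoints regardless of switch, give censoring at switch as a supplementary analysis, and state the number of switchers. A switch should not be coded as a relapse, since that would misclassify patients who switched without one.

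The cost is a short amendment, an added eCRF item and some extra chart extraction. The study is non-interventional and its data come from medical charts, so nobody's care changes. The drawback is that outcomes after a switch also reflect the new drug: in the simulation, ARR with full follow-up stays at 0.14 if the new drug leaves the relapse rate unchanged, and is about 0.12-0.135 if it halves it (an assumption). The supplementary analysis addresses this.

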## 7 EVALUATION CRITERIA

### 7.1 Primary endpoint

- ARR at 48 months

### 7.2 Secondary endpoints

- Proportion of relapse-free patients at 24 and 48 months
- ARR at 24 months
- The time to sustained progression of disability from baseline up to 24 and 48 months
- Time to the first relapse from baseline up to 48 months
- Time to the second relapse from baseline up to 48 months

- Changes in mean number of T1 Gd+ lesions per MRI scan taken at 12, 24, 36 and 48 months compared to baseline
- Changes in mean number of active T2-weighted lesions per MRI scan taken at 12, 24, 36 and 48 months compared to baseline
- Changes in level of disability as measured by EDSS at 6, 12, 18, 24, 30, 36, 42 and 48 months compared to baseline
- No evidence of disease activity (NEDA-3) at 24 and 48 months
- The proportion of patients receiving rescue therapy according to local standards of care from baseline up to 48 months
- Patient adherence to Cladribine 10 mg tablets treatment after both dosing periods as assessed at 3 and 15 months (by counting used tablets from original packages as patients will be asked to bring them to the site).
- Frequency of adverse events interviewed or reported spontaneously by the patients or as noted on physical, MRI or laboratory examinations up to month 48
- Percentage of patients with at least 1 Common Terminology Criteria for Adverse Events (CTCAE) grade 3 or 4 Lymphocyte Toxicity up to month 48
- Median time to recovery from grade 3 or 4 Lymphocyte Toxicity
- Percentage of patients who developed herpes zoster infections or malignancies up to month 48

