### 6.3.1 Inclusion Criteria

- Age  $\geq$ 18 years.
- Patients for whom start of Cladribine 10 mg tablets therapy for highly active relapsing MS (relapsing-remitting multiple sclerosis – RRMS, or secondary progressive multiple sclerosis - SPMS) has been indicated independently before signing informed consent.
- Patient fulfils following local indication criteria for Cladribine 10 mg tablets treatment as applicable in standard of care:
  - 1 severe relapse treated by corticosteroids or EDSS score increase by at least 1 grade during the previous year and at least 1 T1Gd+ lesion or 9 or more T2 lesions during the treatment by at least one other DMD,
- OR
- 2 or more disability causing relapses treated by corticosteroids during the previous year and treated or untreated by the other DMD. MS diagnosis has to be confirmed by cerebrospinal fluid examination.
- Signed informed consent.
- Ability to communicate with investigator and study staff and to comply with their instructions for the entire length of the study participation

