## 8 DATA COLLECTION

### 8.1 Data source

Patients' medical charts, any relevant diagnostic reports including description of MRI scans recorded as part of the standard of care and number of actually used Cladribine 10 mg tablets for adherence evaluation as described in section 5.1 are the source documents for study data collection. Clinical information recorded in patients' medical charts and/or diagnostic reports will be entered into the eCRF (Electronic case report form).

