### 8.2 Collected Data

#### V1 - Pre-dose Year 1 Visit

Date of visit, date of ICF signature (if different), meeting of eligibility criteria (yes/no)

Basic demographic data:

- Year of birth
- Gender

Baseline characteristics:

- Relevant medical history
- Relevant concurrent diseases/concomitant medications

Condition of MS:

- Date of MS diagnosis
- Medical history related to MS
- Previous MS therapy
- Number of relapses in the last 12 months
- Current EDSS score
- Current MRI status (within 3 months)

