**Assessment before therapy initiation (all answers have to be yes)**

- Lymphocyte count must be normal before initiating Cladribine 10 mg tablets in year 1
- MRI should be performed before initiating Cladribine 10 mg tablets (usually within 3 months) to exclude progressive multifocal leukoencephalopathy (PML)
- Patient weight
- Lymphocyte count
- Number of Cladribine 10 mg tablets to be used in the whole treatment course year 1

**V2 - Visit Month 3 Year 1** (2 months after the first dose of Cladribine 10 mg tablets in Year 1)

- Visit date
- Date of Cladribine 10 mg tablet therapy start
- Number of Cladribine 10 mg tablets really used in the whole treatment course year 1
- Lymphocyte count
- Any relapse and rescue therapy from the last visit
- Any AE from the last visit
- Concomitant medication (only corticosteroids, myorelaxants, analgesics, antidepressants, anxiolytics) from the last visit

**V3 - Visit Month 7 Year 1** (6 months after the first dose of Cladribine 10 mg tablets in Year 1)

- Visit date
- Lymphocyte count
- EDSS score
- Any relapse and rescue therapy from the last visit
- Any AE from the last visit
- Concomitant medication (only corticosteroids, myorelaxants, analgesics, antidepressants, anxiolytics) from the last visit

**V4 - Pre-dose Year 2** (12 months after the first dose of Cladribine 10 mg tablets in Year 1; For patients with lymphocyte count below 800 cells/mm^3 the treatment course in year 2 must be delayed for up to 6 months to allow for recovery of lymphocytes as per SmPC. For these patients V4 will be postponed until recovery - up to maximum of 6 months).

- Visit date
- Is patient eligible to continue Cladribine 10 mg tablets therapy as per SmPC? (yes/no)

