**Assessment before therapy initiation (all answers have to be yes)**

- Lymphocyte count must be at least 800 cells/mm^3 before initiating Cladribine 10 mg tablets in year 2
- MRI should be performed before continuing Cladribine 10 mg tablets to exclude PML (within 3 months)
- MRI status
- EDSS score
- Patient weight
- Lymphocyte count
- Number of Cladribine 10 mg tablets to be used in the whole treatment course year 2
- Any relapse and rescue therapy from the last visit
- Any AE from the last visit
- Concomitant medication (only corticosteroids, myorelaxants, analgesics, antidepressants, anxiolytics) from the last visit

**V5 - Visit Month 3 Year 2** (2 months after the first dose of Cladribine 10 mg tablets in Year 2)

- Visit date
- Date of Cladribine 10 mg tablet therapy start
- Number of Cladribine 10 mg tablets really used in the whole treatment course year 2
- Lymphocyte count
- Any relapse and rescue therapy from the last visit
- Any AE from the last visit
- Concomitant medication (only corticosteroids, myorelaxants, analgesics, antidepressants, anxiolytics) from the last visit

**V6 - Visit Month 7 Year 2** (6 months after the first dose of Cladribine 10 mg tablets in Year 2)

- Visit date
- Lymphocyte count
- EDSS score
- Any relapse and rescue therapy from the last visit
- Any AE from the last visit

- Concomitant medication (only corticosteroids, myorelaxants, analgesics, antidepressants, anxiolytics) from the last visit

**V7 - Visit Month 12 Year 2/Month 1 Year 3** (12 months after the first dose of Cladribine 10 mg tablets in Year 2)

- Visit date
- MRI status
- EDSS score
- Any relapse and rescue therapy from the last visit
- Any AE from the last visit
- Concomitant medication (only corticosteroids, myorelaxants, analgesics, antidepressants, anxiolytics) from the last visit

**V8 - Visit Month 7 Year 3** (18 months after the first dose of Cladribine 10 mg tablets in Year 2)

- Visit date
- EDSS score
- Any relapse and rescue therapy from the last visit
- Any AE from the last visit
- Concomitant medication (only corticosteroids, myorelaxants, analgesics, antidepressants, anxiolytics) from the last visit

**V9 - Visit Month 12 Year 3/Month 1 Year 4** (24 months after the first dose of Cladribine 10 mg tablets in Year 2)

- Visit date
- MRI status
- EDSS score
- Any relapse and rescue therapy from the last visit
- Any AE from the last visit

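### The change from baseline in active T2 lesions rests on a baseline count with no defined or listed reference scan, so it mixes scan spacing with disease activity

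*Protocol*

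**What the plan says.** Section 7.2 of the protocol, repeated in the protocol summary, gives the endpoint as "Changes in mean number of active T2-weighted lesions per MRI scan taken at 12, 24, 36 and 48 months compared to baseline". T1 Gd+ lesions are a separate endpoint with the same four time points. Neither place defines active or names the scan against which activity is judged.

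At V1, section 8.2 lists one imaging item, "Current MRI status (within 3 months" before treatment. The only other V1 item that might hold earlier imaging is "Medical history related to MS", which is not broken down further. Table 8-1 shows one MRI before treatment, then MRI at V4, V7, V9 and end of study. No visit list names a scan date, a reference scan or an inter-scan interval.

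Scan timing follows routine care. Section 5.1 states "There is no assessment mandated per study protocol", and section 8.1 names as a source the "description of MRI scans recorded as part of the standard of care". V4 is nominally 12 months after the first dose, but for patients with slow lymphocyte recovery section 8.2 says "For these patients V4 will be postponed until recovery - up to maximum of 6 months". The V4 checklist adds "MRI should be performed before continuing Cladribine 10 mg tablets to exclude PML (within 3 months" as its window.

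**The concern.** A count of T1 Gd+ lesions can be read from a single scan. A count of new or enlarging T2 lesions cannot: it needs two scans, and it grows with the time between them. At follow-up the second scan is at hand, because each study scan has a predecessor in the study. At baseline it is not. The reference could be a scan a few months old, a scan two years old, or none.

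The endpoint then subtracts a count built up over an unspecified interval from one built up over roughly a year. The study is single-arm, so no comparator carries the same distortion and cancels it. A reader shown a fall or a rise in active T2 lesions could not tell how much came from lesion formation and how much from the spacing of routine scans.

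**Working it through.** The protocol states no expected value for this endpoint, so there is no figure to reproduce. The check asks how far spacing alone can move the result.

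**Inputs**
- b, months from the reference scan to the baseline scan: not given. Assumed range 3 to 24.
- f, months from the previous study scan to the follow-up scan: nominally 12, from the visit schedule in section 8.2.
- Lesion rate r: not given. Assumed 2 per year, with 1 per year as a second case.
- Active taken to mean new or enlarging since the reference scan (an assumption; see section 7.2).

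**Spacing allowed by the protocol.** Take V1 as close to the first dose. The baseline scan may be up to 3 months before V1, V4 may move up to 6 months later, and the V4 scan may be up to 3 months before treatment continues.
- V1 to V4, shortest: 12 - 3 = 9 months.
- V1 to V4, longest: 12 + 6 + 3 = 21 months.
- V4 to V7, which is set 12 months after the first year-2 dose: 12 to 12 + 3 = 15 months.

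**Formula.** Expected count = rate x interval / 12, so

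expected change = r(follow-up) x f/12 - r(baseline) x b/12.

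**Results with f = 12**

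| b (months) | Baseline count at 2/year | Change, rate stays 2/year | Change, rate halves to 1/year |
|---|---|---|---|
| 3 | 0.5 | 2 - 0.5 = +1.5 | 1 - 0.5 = +0.5 |
| 6 | 1.0 | 2 - 1 = +1.0 | 1 - 1 = 0 |
| 12 | 2.0 | 2 - 2 = 0 | 1 - 2 = -1.0 |
| 18 | 3.0 | 2 - 3 = -1.0 | 1 - 3 = -2.0 |
| 24 | 4.0 | 2 - 4 = -2.0 | 1 - 4 = -3.0 |

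At a constant 1 per year the changes are half as large: +0.75, +0.5, 0, -0.5 and -1.0.

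With no true change, b = 24 looks like a 50% fall (4 to 2) and b = 6 like a doubling (1 to 2). With a true halving, b = 6 looks like no change and b = 3 like a doubling (0.5 to 1).

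**Effect of the first follow-up interval alone.** Hold b at 12 and the rate at 2 per year:
- f = 9: 1.5 - 2 = -0.5.
- f = 18: 3 - 2 = +1.0.
- f = 21: 3.5 - 2 = +1.5.

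**After dividing each count by its interval.** A constant rate gives 0 and a halving gives -1.0 lesion per year (-50%), whatever b and f are.

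**The case against.** The strongest reply is that much of this belongs elsewhere. Section 12 promises a SAP, section 5.1 says the statistician will assign assessments to visit windows, and section 9.1 puts the eCRF instructions in a separate document. Defining active, choosing the comparator scan and annualising are commonly settled there. The eCRF fields under the MRI and MS-history items are not shown, and routine reports are a named source, so earlier scan dates may be retrievable. The endpoint is also one descriptive secondary measure; the primary is the annualised relapse rate.

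Part of this stands. It limits the weight of the point, and it rules out saying that no reference scan is collected: what can be said is that none is listed. It does not remove the point. The protocol itself fixes the contrast with baseline. A visit window decides which scan counts as month 12, but does not fix the interval behind the baseline count. A SAP can define active, but it may be unable to supply reference dates that sites were not asked for, and section 12 requires its approval only before the database closes.

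Three stronger readings are tempting and should be resisted.
- *The change shows scan spacing instead of disease activity.* It shows both. With b and f near 12 months it tracks activity.
- *The endpoint exaggerates benefit, because patients without an earlier scan have their whole lesion load counted as active.* Nothing in the protocol says this, and a short reference interval would push the result the other way.
- *Untreated entrants have no earlier scan.* Section 6.3.1 admits such patients by one route but is silent on their imaging.

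The other entry route does not settle the matter either. It asks for "at least 1 T1Gd+ lesion or 9 or more T2 lesions during the treatment by at least one other DMD". That may imply earlier imaging for some patients, but it is a lesion count, not a dated count of new or enlarging lesions, and the scan that meets it could be the baseline scan itself.

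**Conclusion.** The point holds in limited form. The baseline active T2 count has no defined or listed reference scan or interval, while follow-up counts have a natural reference nominally 12 months earlier, or about 9 to 21 months earlier at V4. On the usual meaning of active, the stated change is confounded by scan spacing.

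Over the assumed range of 3 to 24 months before baseline, spacing alone moves the expected change from +1.5 to -2.0 lesions at 2 per year. A true halving with evenly spaced scans gives -1.0, so the distortion can match or exceed a substantial effect. These figures illustrate scale and do not estimate bias in this cohort. They rest on the assumed rate, the assumed pre-baseline interval, counts accruing in proportion to time, and V1 lying close to the first dose. The actual direction and size cannot be known from the documents.

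The problem is confined to the T2 contrast with baseline. T1 Gd+ counts need no reference scan, and comparisons among follow-up scans are less affected. For a secondary endpoint in a single-arm study, this should be corrected but does not threaten the main result.

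**What to change.** In section 7.2, define active T2 lesions as new or enlarging against the preceding study scan. Report them at 12, 24, 36 and 48 months per year of actual inter-scan interval. Add the date of every MRI to the items collected in section 8.2.

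Keep the before-after MRI contrast for T1 Gd+ lesions. If a baseline active T2 contrast is wanted, add the date of the earlier reference scan at V1, express both sides as annualised rates, limit the contrast to patients with a dated earlier scan, and state how many there are.

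The cost is wording plus date fields, to be filled from routine reports where these carry the dates. No additional scan or visit is needed. The downside is a smaller or absent before-after T2 figure for patients without a dated earlier scan. Annualising also leaves one limit: the first follow-up count will include any lesions formed between the baseline scan and the first dose.
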